13.3. Appendix 3: Assessment Windows

13.3.1. Definitions of Assessment Windows for Analyses

Laboratory data, vital signs, ECGs, health outcomes assessments, and genotypic/phenotypic data will be assigned to assessment windows according to actual dates rather than the nominal visit labels as recorded on the eCRF or in the laboratory database.

In most cases the window around an assessment will include all dates from the midpoints between the target day and that of the previous and the proceeding visits. In general, the nominal target study day for week w is $(7*w) + 1$.

For parameters which are not scheduled to be assessed at particular visits, the all-inclusive assessment windows will still be used; however, data summaries will only report scheduled visits. Assessments at unscheduled visits will be included for ‘any time On-treatment’ time points and in data listings, as well any algorithms that make use of additional data (e.g., Snapshot).

Prior to visit slotting, assessments are first assigned to a study phase (screening, maintenance, extension, or Long Term Follow Up) based on the Tables in Section 13.4.1 and treatment state based on Section 13.4.2.

Maintenance phase assessments are assigned based on the Maintenance Phase Study Day as shown in Table 9. The analysis visits from Week 4 to Week 52 should be only applied to the assessments that are already assigned to Maintenance phase (on-treatment). Extension phase assessments are assigned based on the Maintenance Phase Study day for subjects continuing Q4W IM dosing into the Extension Phase, and based on the Extension Phase Study Day for subjects switching from the control arm to Q4W IM dosing for the Extension phase as shown in Table 10. The analysis visits from Week 56 (except for Follow-up) in the Extension phase should be only applied to the assessments that are already assigned to Extension phase (on-treatment).

Long-term Follow-up phase assessments are assigned based on the LTFU study day as shown in Table 12. The analysis visits in LTFU should be only applied to the assessments that are already assigned to LTFU phase regardless of treatment state. See Section 13.6.1, for derivation of Maintenance, Extension and LTFU Study Day.

13.3.2. Definitions of Assessment Windows for Data Other than Health Outcome and PK

Table 9 Assessment Windows for Screening & Maintenance Phase Data

Parameters[d] collected in sparse visit [c]	Analysis Window	Target Study Day	Analysis Timepoint
	Study Day ≤ 1 (the first record if there are multiple values)	The day of earliest record	Screening
	Last available recorded value up to and	1	Baseline

Parameters[d] collected in sparse visit [c]	Analysis Window	Target Study Day	Analysis Timepoint
	including the date of first maintenance phase dose of IP		
ECG, CD8, CD4/CD8 ratio	2 ≤ Study Day ≤ 70	29	Week 4
	2 ≤ Study Day ≤ 42		
	43 ≤ Study Day ≤ 70	57	Week 8
	71 ≤ Study Day ≤ 98	85	Week 12
	99 ≤ Study Day ≤ 126	113	Week 16
	127 ≤ Study Day ≤ 154	141	Week 20
urinalysis, CD8, CD4/CD8 ratio	155 ≤ Study Day ≤ 210	169	Week 24
	155 ≤ Study Day ≤ 182		
	183 ≤ Study Day ≤ 210	197	Week 28
	211 ≤ Study Day ≤ 238	225	Week 32
	239 ≤ Study Day ≤ 266	253	Week 36
	267 ≤ Study Day ≤ 294	281	Week 40
	295 ≤ Study Day ≤ 322	309	Week 44
	ECG, CD8, CD4/CD8 ratio, urinalysis, lipids, bone and renal markers	323 ≤ Study Day ≤ 378	337
323 ≤ Study Day ≤ 350			
	For 'Current ART' arm; 351 ≤ Study Day ≤ Maintenance Current ART Stop Day ^[b] + 1 For 'Q4W' arm: 351 ≤ Study Day ≤ Max (Day of Last Q4W IM Dose + 35, Last Oral dose Day + 1) ^[a]	365	Week 52
	For subjects who discontinued from oral lead-in during Maintenance phase, Study Day > (Day of last oral lead-in dose+1) Subjects discontinued from Current ART and not continuing into extension phase Study Day > (Maintenance Current ART Stop Day ^[b] + 1)		Follow-up

[a] Last Q4W IM / last oral dose is only applied to subjects who permanently discontinue from study treatment

[b] Current ART stop day: the last permanently stop day among all ARTs taken during Maintenance phase.

[c] For parameters with sparse collection, post baseline data will only be slotted to those specific analysis windows. The Screening or Baseline slotting will be based on the same rules as all other lab parameters use.

[d] **Urinalysis:** Urine Albumin/Creatinine, Urine Creatinine, Urine pH, Urine Protein/Creatinine, Urine Erythrocytes, Urine Specific Gravity, Urine Leukocytes, Urine Retinol Binding Protein, Urine Phosphate, Urine Creatinine

Bone marker: Bone Specific Alkaline Phosphatase, Osteocalcin, Procollagen 1 N-Terminal Propeptide, Vitamin D, Type I C-Telopeptides

Renal marker: Cystatin C, Retinol Binding Protein

13.3.3. Assessment Window for Study Conclusion

The ‘Phase conclusion’ records in disposition data will be slotted based on [Table 9](#) and [Table 10](#). However, for the record of ‘Phase Conclusion’, if a discontinuation date is post-treatment, then it will be slotted to the last on-treatment visit within the same treatment phase rather than follow up.

13.3.4. Assessment Window for Health Outcome Data

13.3.4.1. NRS

NRS questionnaire assessments are assigned to analysis visits based on the windows defined in [Table 13](#).

Table 13 Assessment Windows for Maintenance Phase NRS Questionnaire Data

Domain	Parameter	Target Date	Analysis Window	Analysis Timepoint
NRS	All	Date of 1 st Injection	Assessment Date \leq Date of 1 st injection + 2	Week 4
		Date of 1 st injection+7	Date of 1 st injection + 3 \leq Assessment Date \leq Date of 1 st injection + 42	Week 5
		Date of W40 Injection	If participant received Week 40 injection: Date of WK40 injection - 42 \leq Assessment Date \leq Date of W40 Injection + 2	Week 40
		Date of 1 st Injection + 252	If participant did not receive Week 40 injection: Date of 1 st injection + 210 \leq Assessment Date \leq Date of 1 st injection + 280	

Domain	Parameter	Target Date	Analysis Window	Analysis Timepoint
		Date of W40 Injection + 7	If participant received Week 40 injection: Date of W40 Injection + 3 ≤ Assessment Date ≤ Date of W40 Injection + 28	Week 41
		Date of 1 st Injection + 308	If participant received Week 40 injection: Date of 1 st Injection + 280 < Assessment Date ≤ Date of 1 st Injection + 350 AND Assessment Date > Date of WK40 injection + 28	Week 48
		Date of 1 st Injection + 308	If participant did not receive Week 40 injection: Date of 1 st Injection + 280 < Assessment Date ≤ Date of 1 st Injection + 350	

Note: Apply NRS analysis windows only to assessments that are on-treatment (per [Table 20](#)) within the Maintenance phase (Per [Table 17](#))

13.3.4.2. PIN/HATQoL/SF-12/HIVTSQs/HIVTSQc/ACCEPT/Treatment Preference

PIN, HATQoL, SF-12, HIVTSQs, HIVTSQc, ACCEPT, Treatment Preference, Willing to Switch questionnaire assessments will be assigned to analysis visits as follows:
 Baseline: Baseline will be defined as last available recorded value up to and including the date of first maintenance phase dose of study treatment.

Post-Baseline nominal visit: There will be no slotting for Post-baseline planned nominal visits (i.e. analysis visit =visit). The post-baseline planned nominal visits for each questionnaire are listed in [Table 14](#).

Withdrawal/unscheduled post-baseline visit at Maintenance phase (per [Table 17](#)) will be slotted per the following slotting steps:

- Identify the ‘last nominal visit’ with the HO assessment performed prior to the unscheduled/withdrawal visit to be slotted during the Maintenance phase
- The unscheduled/withdrawal visit will be slotted to the planned nominal visit subsequent to the ‘last nominal visit’ during the Maintenance phase

Example 1, for HATQoL, the post-baseline planned nominal visits are Week 24, 48, and 96. If a subject has the ‘last nominal visit’ (with HATQoL assessment) at Week 24 prior to withdrawal at Week 36, the withdrawal assessment will be slotted to the subsequent planned nominal visit of Week 48.

Example 2, for HATQoL, if there is unscheduled visit between Week 24 and Week 48. This unscheduled visit will be slotted to Week 48 per the rule. In this case, there are two assessments with analysis visit equal to Week 48 (i.e. the slotted value and the value at

original nominal week 48 visit). The original nominal value will be selected for summary per the rule below for multiple records.

Table 14 Planned Nominal Visit of Health Outcome Data at Maintenance phase

Endpoints	Day1	WK4B	WK5	WK8	WK24	Wk40	WK41	WK44	WK48	WK52
PIN (Q4W)			X				x		x	
HATQoL	x				x				X	
SF-12	x				x				x	
HIVTSQs	x	X			X			x		
HIVTSQc									x	
ACCEPT	x			x	x				x	
NRS (Q4W)		X	x			X	x			
Treatment preference									x	
Willing to switch	X (Q4W)									x (CAR)

13.3.4.3. Evaluable Criteria for Observed Case Displays – PIN and NRS only

Post the visit slotting as described above, data that is assessed outside of 5-9 days post injection at Week 5/41 for NRS/PIN, and data at Week 4b/40 for NRS that is not assessed on the same day as CAB+RPV injections are received will be excluded from Observed Case Displays (see Table 14). However, these data will still be used for LOCF Displays.

Table 15 Evaluable Criteria using Time Window for non-LOCF summaries

Endpoints	WK4B	WK5	Wk40	WK41
PIN (Q4W)		X (within Day 5-9 post injection)		X (within Day 5-9 post injection)
NRS (Q4W)	X (on the same day of WK4B injection)	X (within Day 5-9 post injection)	X (on the same day of WK4B injection)	X (within Day 5-9 post injection)

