To assess treatment acceptance	
 Change from Baseline in treatment acceptance at Week 8, Week 24, Week 48, Week 96 (or Withdrawal) using the “General acceptance” dimension of the Chronic Treatment Acceptance (ACCEPT) questionnaire
To assess tolerability of injections	
 Change from Week 4b in tolerability of injection at Week 5, Week 40, Week 41, and Week 96 using the Numeric Rating Scale (NRS) within the CAB + RPV LA arm.
Exploratory Objectives	Exploratory Endpoints
To explore the effect of patient characteristics (e.g., demographic factors, Baseline CD4+) on the virologic and immunologic responses to CAB LA+ RPV LA compared to continuation of current ART	
 Proportion of participants by patient subgroup(s) (e.g., by age, gender, BMI, race, HIV-1 subtype, Baseline CD4+) with Virologic Failure over time including Week 48 using the Snapshot algorithm for the ITT-E population Proportion of participants by patient subgroup(s) (e.g., by age, gender, body mass index (BMI), race, HIV-1 subtype, Baseline CD4+) with plasma HIV-1 RNA <50 c/mL over time including Week 48 using the Snapshot algorithm for the ITT-E population Change from Baseline in CD4+ cell counts by subgroups at Week 48
To explore relationship(s) between plasma concentrations of CAB and RPV and pharmacodynamic endpoints.	
 Relationship between plasma PK concentrations and virologic, immunologic responses, and/or occurrence of adverse events [AEs] over time may be explored.
To evaluate renal and bone biomarkers in participants treated with CAB LA + RPV LA compared to continuation of current ART	
 Absolute value and change from Baseline in renal (in urine and blood), and bone (in blood) over time
To assess preference for CAB LA+ RPV LA compared to oral ARV using a single dichotomous preference question.	
 For patients randomized to the “CAB LA + RPV LA” arm, preference for CAB LA + RPV LA compared to oral ARV regimen, at Week 48 For patients randomized to the “Current ART” arm who switched to the injectable treatment, preference for CAB LA + RPV LA compared to current ART regimen at Week 96 (end of extension phase-secondary analysis)

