- If a subject with CDC 'Stage II' at baseline had the lowest post-baseline CD4+ =220 cell/mm³ AND had at least one new AIDS-defining condition, then HIV disease progression for this subject would be considered as 'CDC stage II at baseline to CDC stage III'.

Delay in IP Injection

IM dosing is expected to occur every 4 weeks from Week 4b onwards. The Delay in IP injection (days) will be calculated as below:

- Delay in IP injection(days) = Injection date - date of preceding injection – 28 days

Delay in IP injection will be grouped into: ≤1, 2-3, 4-7, >7 days.

The proportion of subjects with HIV-1 RNA ≥50 c/mL at Week 48 (Snapshot) will be summarized by last delay in IP Injection. The last delay in IP injection will be the delay in IP injection at Week 48, or the delay in last IP injection prior to Week 48 if a subject does not receive Week 48 injection (i.e. missing visit or withdrawal).

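### Table 15 ties the Week 40 NRS to the Week 4B injection, contradicting the prose above it; coded literally, it would leave no Week 40 score in the observed-case displays.

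*SAP*

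**What the plan says.** Section 2.2 lists as a secondary endpoint, within the CAB + RPV LA arm, "Change from Week 4b in tolerability of injection at Week 5, Week 40, Week 41, and Week 96" on the Numeric Rating Scale (NRS).

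Section 13.3.4.3 then sets the evaluability criteria for the observed-case displays of PIN and NRS. Its prose says that "data at Week 4b/40 for NRS that is not assessed on the same day as CAB+RPV injections are received will be excluded" from those displays, and refers the reader to Table 14. It adds: "However, these data will still be used for LOCF Displays".

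Table 15 follows, headed as the evaluability criteria for the non-LOCF summaries. In its NRS row, the Week 4B and Week 40 cells carry the same entry: "X (on the same day of WK4B injection". The prose therefore applies one same-day rule to both visits, while the table ties both visits to the first injection.

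**The concern.** A Week 40 score is taken months after the Week 4B injection and cannot fall on the same day. The table and the prose therefore give opposite answers for an ordinary, on-schedule Week 40 assessment.

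Table 14 plans the NRS at Weeks 4B, 5, 40 and 41 in the Maintenance Phase. Only Weeks 4B and 40 are injection-day scores, since Weeks 5 and 41 are assessed about a week after injection. Week 4B to Week 40 is thus the only planned injection-day comparison in that phase. A programmer working from Table 15 would lose it from the two observed-case displays in section 13.13.9: 7.35 (scores by visit) and 7.37 (change from Week 4B).

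The LOCF versions are not a full substitute. They keep scores that fail the evaluability criteria, and under section 13.7.2.2 they carry an earlier on-treatment value forward where one is missing.

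**Working it through.** **Inputs**

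- Injection schedule (section 13.6.4): "IM dosing is expected to occur every 4 weeks from Week 4b onwards". The Week 4B injection is therefore the first injection.
- Week 40 NRS window in Table 13 (section 13.3.4.1), Week 40 injection received: it opens at "Date of WK40 injection - 42" days and closes 2 days after that injection.
- Week 40 NRS window in Table 13, Week 40 injection not received: it opens at "Date of 1 st injection + 210" days, with target "Date of 1 st Injection + 252" days.
- Week 4 NRS window in Table 13: every assessment up to 2 days after the first injection.

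**Step 1: reproduce the plan's own figure.** First injection to Week 40 = 7 × (40 − 4) = 252 days, or nine 28-day intervals. This agrees with the Table 13 target.

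**Step 2: can a Week 40 score fall on the day of the first injection?**

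- Week 40 injection given on schedule: the window opens 252 − 42 = 210 days after the first injection.
- Week 40 injection not given: the window opens at first injection + 210 days by definition.
- For the window to reach back to the first injection, the Week 40 injection would have to come within 42 days of it, against a planned 252.
- An NRS taken on the day of the first injection already falls in the Week 4 window.

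The condition in the Week 40 cell therefore cannot be met by any score slotted to Week 40 on schedule.

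**Step 3: one participant under each rule.** Take the first injection on Study Day 29 (7 × 4 + 1), and the Week 40 injection and NRS both on Study Day 281 (7 × 40 + 1).

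| Rule | Day required | Day of NRS | Evaluable? |
|---|---|---|---|
| Prose of 13.3.4.3 | 281 | 281 | Yes |
| Table 15, literal | 29 | 281 | No |

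**Step 4: which outputs are touched.** The observed-case displays 7.35 and 7.37 are touched. Displays 7.34, 7.36 and 7.38 are LOCF and keep the scores. Table 7 plans no statistical analysis of the NRS, section 10.6 does not model it, and section 5.5.2 does not list it among the key secondary comparisons.

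**The case against.** The strongest reply is that the intended rule is hardly in doubt. The prose applies the same-day requirement to Week 40 in so many words. Table 13 sets the Week 40 target at the date of the Week 40 injection. The notes to the schedule in section 13.2.1 have the NRS given about 30 to 60 minutes after injections. Only one cell disagrees, it duplicates its neighbour, and its condition is impossible. A program that followed it would return an empty Week 40 column, which output review should catch, rather than a plausible wrong number.

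Most of this stands. A reader looking only at Table 15 might infer that the plan excludes every Week 40 score from the observed-case displays. The document as a whole does not support that reading, because the sentence above the table gives a rule that can be met. Total exclusion is the result of one literal reading, not the plan's settled effect.

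The reply does not remove the contradiction. Table 15 is the compact specification for exactly these displays, and nothing says that the prose prevails over it. The reference to Table 14 is not plainly false, since that table lists the planned visits, but it does not lead the reader to the criteria.

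**Conclusion.** The Week 40 NRS cell of Table 15 is wrong as written and contradicts the prose of the same section. Under a literal reading of the table, no Week 40 NRS score is evaluable, and displays 7.35 and 7.37 lose that visit. Under the prose, scores taken on the day of the Week 40 injection stay in.

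The consequence is small. Both displays are descriptive and cover only the Q4W IM arm. The LOCF displays, the primary analysis and every tested endpoint are unaffected.

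This rests on two assumptions. One is that injections run roughly to schedule; only a Week 40 injection within 42 days of the first would bring the two dates into one window. The other is that the prose, which does not name the visit, means the injections given at the visit being scored. The Table 13 target for Week 40 supports that. A copying slip from the Week 4B cell is the likely cause, though the document does not say so.

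**What to change.** Change the Week 40 NRS cell of Table 15 to require assessment on the same day as the Week 40 injection, so that table and prose agree. In the prose, cite Table 15, where the evaluability criteria are, as well as or instead of Table 14.

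The cost is one table cell and one cross-reference. No data collection, visit or analysis method changes. If the displays have already been programmed, check that the Week 40 flag was derived from the Week 40 injection date.

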13.3.5. Assessment Window for PK concentration Data

For PK concentration data at the withdrawal/unscheduled/LTFU Month1 visits during Maintenance or Extension phase, the visit will be slotting to the analysis visit per the following steps:

- Identify the ‘last nominal visit’ with the PK pre-dose assessment performed prior to the visit to be slotted during the same study phase
- The unscheduled/withdrawal/LTFU Month1 visit will be slotted to the nominal visit corresponding to the earliest of the next planned injection visit or next planned PK assessment visit (excluding timepoints with storage PK collection), that is subsequent to the ‘last nominal visit’ during the same study phase.

During Maintenance or Extension phase, the planned nominal visits for PK Pre-dose are Week 4b, 8, 12, 16, 20, 24, 28, 32, 36, 40, 44, 48, 52, 96 for Q4W arm; and are Week 56b, 60 for Current ART arm.

For example, if a subject has the ‘last nominal visit’ (with PK pre-dose assessment) at Week 24 and then withdraws (around Week 28) with a PK assessment labelled at ‘LTFU month1’ post Week 24 during the Maintenance phase, this assessment will be slotted to the subsequent planned nominal visit of Week 28.

There will be no slotting for planned nominal visits (i.e. analysis visit =visit).

13.3.6. Multiple assessments within an Analysis Window

If after window assignment there are multiple valid assessments of a parameter within the same window, then the following hierarchy will be used to determine the value to be used for summary statistics of observed values:

For data other than health outcome/PK concentration

1. the assessment closest to the window target Study Day;
2. if there are multiple assessments equidistant from the target Study Day, then the mean of these values will be used. For HIV-1 RNA, the geometric mean of the number of copies will be used as opposed to the arithmetic mean.

For Health outcome (excluding NRS) and PK concentration data,

1. If there are multiple assessments assigned to the same analysis visit, the assessment from the planned nominal visit will be used for summary statistics.

For NRS questionnaire assessments:

1. the assessment closest to the window target date will be used;
2. if there are multiple assessments equidistant from the target date, then the earliest assessment will be used.

Assessments not chosen for use in summary statistics by this algorithm will still appear in the associated listings. Also, such valid assessments will be used when determining values of potential clinical concern for the ‘any time On-treatment’ time point, and for any algorithm that has specific rules for which observation to use (e.g., snapshot algorithm or LOCF)

13.4. Appendix 4: Study Phases and Treatment State

13.4.1. Study Phases

Assessments and events will be classified according to the time of occurrence relative to the Treatment Start Date defined in Section 13.6.1.

AEs will be assigned to study phases as defined in Table 16. For example, adverse events prior to start of Extension phase IP/LTFU ART will be assigned to the Maintenance Phase.

Laboratory data (efficacy, safety, and virology), HIV associated Conditions, health outcomes assessments, vital signs, and ECGs will be assigned to study phases as defined as in Table 17. For example, assessments/events occurring up to and including start of extension phase IP/LTFU ART will be assigned to the Maintenance Phase.

Assessments/events are assigned to study phases sequentially, starting from the top of each table.

Table 16 Assignment of Study Phases for AEs

Study Phase	Date range
Screen	Date < Maintenance Treatment Start Date
Maintenance	Current ART Arm: For subjects continuing into Extension Phase: Maintenance Treatment Start Date ≤ Date ≤ Start Date of Extension Phase with Oral lead-in of CAB + RPV (expected to be WK52) -1 For subjects not continuing into Extension Phase: Date ≥ Maintenance Treatment Start Date
	Q4W IM Arm: For subjects continuing into Extension Phase: Maintenance Treatment Start Date ≤ Date ≤ date of Nominal Week 52 Visit-1 (i.e. the day before Nominal Week 52 Visit). For subjects not continuing into Extension Phase: Maintenance Treatment Start Date ≤ Date ≤ LTFU ART Start Date -1
Extension	Subjects Switching from Maintenance Control Arm to Q4W: Start Date of Extension Phase Oral lead-in of CAB + RPV ≤ Date ≤ LTFU ART Start Date -1 Subjects continuing maintenance Q4W into Extension phase Date of Nominal Week 52 Visit ≤ Date ≤ LTFU ART Start Date -1

- **Date** = AE Start date
- **Maintenance Treatment Start Date:** refer to Treatment Start Date in Section 13.6.1

Table 17 Assignment of Study Phases for Lab assessments (including PK), ECG, Vital Sign, and HIV associated conditions

Study Period	Date range
Screen	Date ≤ Maintenance Treatment Start Date
Maintenance	Current ART Arm: For subjects continuing into Extension Phase: Maintenance Treatment Start Date < Date ≤ Start Date of Extension Phase Oral lead in of CAB + RPV (expected to be nominal Week 52) For subjects not continuing into Extension Phase: Date > Maintenance Treatment Start Date
	Q4W IM Arm: For subjects continuing into Extension Phase: Maintenance Treatment Start Date < Date ≤ Date of Nominal Week 52 visit For subjects not continuing into Extension Phase: Maintenance Treatment Start Date < Date ≤ LTFU ART Start Date
Extension	Subjects Switching from Maintenance Current ART Arm to Q4W IM: Start Date of Extension Phase Oral lead-in of CAB + RPV < Date ≤ LTFU ART Start Date Subjects continuing maintenance Q4W IM into Extension phase Date of Nominal Week 52 Injection < Date ≤ LTFU ART Start Date

- Date = start or assessment date
- Maintenance Treatment Start Date: refer to Treatment Start Date in Section 13.6.1

Table 18 Assignment of Study Phases for Concomitant medication/ART

Concomitant during:	Date range
Maintenance	Current ART Arm: Maintenance Treatment Start Date ≤ Medication Taken < Start Date of Extension Phase Oral CAB + RPV (expected to be Nominal Week 52) or Withdrawn date prior to Extension Phase
	Q4W IM Arms: For subjects not continuing into Extension Phase: Maintenance Treatment Start Date ≤ Medication Taken < LTFU ART Start Date For subjects continuing into Extension Phase: Maintenance Treatment Start Date ≤ Medication Taken < Date of Nominal Week 52 visit
Extension	Date of nominal Week 52 visit ≤ Medication Taken < LTFU ART Start Date

Note: ART stopped on or before the Maintenance Treatment start date will not be assigned to the Maintenance Phase; ART stopped on or before the date of nominal Week 52 visit will not be assigned to Extension phase.

If a partial date for medication/ART is recorded in the eCRF, the following convention will be used to assign the medication:

- if the partial date is a start date, a '01' will be used for missing days and 'Jan' will be used for missing months;
- if the partial date is a stop date, a '28/29/30/31' will be used for the missing day (dependent on the month and year) and 'Dec' will be used for the missing month; for medications recorded separately in the eCRF as prior ART, the earlier of this imputed date or the day before IP start will be used.

The recorded partial date will be displayed in listings.

Table 19 Assignment to Long-Term Follow-Up Phase

Study Phase	Date range
Long-Term Follow-Up	Date > max(Last IM Injection Date, Last Oral Bridging End Date)

- Date = Assessment/Start Date

Note that the long-term follow-up phase and maintenance/extension phases are not necessarily mutually exclusive and are to be defined with separate phase variables in the datasets. For example, an Q4W IM subject who has Week 44 injection and withdrawal at Week 48 without receiving Week 48 injection, the “Week 48 withdrawal visit” belongs to both the maintenance phase and long-term follow-up phase.

In addition to the phases (i.e. Maintenance, Extension, Long term follow up) defined as above, some summaries for AE and LAB data in Q4W IM arm will also be produced for the ‘oral lead-in’ period. The ‘oral lead-in’ period will be defined in separate variables for Q4W IM arm only at maintenance phase, as below:

For AE:

For subjects receiving at least one Maintenance Phase Injection:

Maintenance Treatment Start Date ≤ Date < Date of First IM injection

For subjects withdrawing prior to first Maintenance Phase Injection:

Date ≥ Maintenance Treatment Start Date

For non-AE:

For subjects receiving at least one Maintenance Phase Injection:

Maintenance Treatment Start Date < Date ≤ Date of First IM injection

For subjects withdrawing prior to first Maintenance Phase Injection:

Date > Maintenance Treatment Start Date

